Visit 1: BASELINE visit at the time of recruitment (flexible time point but not within the 4 week period after vaccination)

Visit 2: PRE-VACCINATION visit (omitted if less than 12 weeks after visit 1)

Visit 3: PEAK IMMUNE RESPONSE post vaccination (4-10 weeks after vaccine dose)

Visit 4: LONGEVITY of immune response post vaccination (24-36 weeks post vaccine dose)

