23.0 Appendix 3 Statistical analysis plan

Sample size and randomisation

We have assumed that a sample size of 3000 is feasible and that this is likely to be distributed as 750 in the "low response/no response" group and 2250 in the "normal response" group. We might then wish to estimate what difference between these two groups we could detect with 90% power. We have good estimates from previous studies over time in vulnerable populations and have therefore considered a range of infection and hospitalisation rates that might be plausible for this group. We have also considered the statistically most conservative option by setting the proportion at 50%.

In all cases, we can detect an absolute difference between groups of less than 10% and often less than 5% even for the rarer outcome of hospitalisation. These are consistent with a standardised effect sizes ranging from 0.15 to 0.36 for infection, which are consistent with small to moderate effects. The effect size for hospitalisation is less certain and ranges from 0.24 consistent with a small effect through to 1.33, a very large effect.

We consider this reassuring as it indicates that for a wide range of scenarios, we should have adequate power in the whole cohort for our primary outcome of infection and we may have power to detect a moderate effect for the rarer secondary outcome of hospitalisation, depending on the prevailing population rates and the variant of interest.

We will monitor all the assumptions that underlie these calculations at least monthly and will discuss monthly at our Trial Meeting Groups, if there are any concerns about power for key analyses.

Randomisation procedure

This is an observational cohort and participants will not be randomised. The cohort may be used in future to recruit to randomised trials and the process for selection and randomisation would be described accordingly in the associated trial protocol.

Statistical analysis considerations

Definition of analysis populations

CV groups are defined below and are derived in part from the QCOVID4 risk groups.

The Healthy Control (HC) group represent a population sampled from the PITCH Study (Protective immunity from T-cells in healthcare workers).

Baseline characteristics

At baseline the following characteristics will be described for the study cohort:

- Demographics (Age, BMI, self-reported ethnicity, sex, Index of Multiple Deprivation)

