- · Occupation, nature of work and type of personal protective equipment used during that work
- Medical conditions (self- reported)
- latrogenic immunosuppression (or within 6 months of iatrogenic immunosuppression including chemotherapy)
- · Vaccination history including COVID-19, influenza, and any test vaccines given
- · Known prior infection

Behavioural variables

If the participant self-isolated as a result of an illness in a household contact, we will collect data on the nature of that illness (when was illness, symptoms, severity, duration) and how many other household contacts were unwell.

Serological response

Time points for serological measurements: Assessment at 4 timepoints (Visit 1: baseline visit, Visit 2: before next vaccine dose, visit 3: 4 weeks post vaccine dose and Visit 4: 24-36 weeks post vaccine).

ii) 'Low' antibody range: Antibody values which lie within the lower 10th percentile of range of IgG antibody concentrations in HC following vaccine dose.

General analysis principles

- Summary statistics will include either mean, standard deviation, and/or median, interquartile range for continuous variables as appropriate to the distribution and n (%) for frequencies.
- The amount of missing data will be reported. Analysis will be of complete data and missing data will not be imputed.
- 5% two-sided level of statistical significance, with corresponding 95% confidence intervals presented where applicable.
- No adjustments for multiplicity are planned.

Planned analyses and reporting:

Primary Outcome

To assess the additive value of serological responses to CV status in predicting infection

The binary infection outcome will be captured by recording the timing and incidence rates of all infections from ≥14 days post vaccination given between Visit 2 until Visit 4 will be reported in the total combined CV groups, and by individual CV groups. We will describe the number and proportion of infections for each level of antibody response post-V3 (no, low, normal)

The primary analysis will be undertaken using a logistic regression model with infection as the outcome and antibody response post-V3 as a binary variable as the exposure. We will present odds ratios with 95% confidence intervals for the unadjusted model, as well as for a model adjusted for the baseline and behavioural variables as well as any COVID-19 therapy received in the community, preadmission and in hospital (where data available).

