To assess serological responses, antibody boosting, antibody waning and correlation with infection

The above analyses focus primarily on Visit 3 (4 weeks post vaccine booster). Similar analysis will be performed from antibody status at time point Visit 1, with adjustment required for time post-vaccine to Visit 1, and also vaccine type pre-Visit 1 (Wuhan or bivalent vaccine). Infection outcomes will be described up until Visit 2. Assessment of waning (rate of antibody concentration decline) will also be described between Visit 1 and Visit 2. Assessing differences between HC versus CV group, but also individual groups. Similar waning analysis will be reported between Visit 3 and Visit 4.

Descriptive changes in antibody levels between Visit 3 and Visit 4 by CV groups will also be reported.

Sponsor: University of Birmingham

Antibody binding to VOC

This analysis will be focused on samples derived from Visit 1 and at subsequent follow up points, assuming this will capture most diversity in VOC during the study duration. Antibody binding to SARS-CoV-2 WT will be compared against binding to the dominant VOCs in participants with detectable antibodies and reported as fold-change (e.g. VOC/WT) and absolute change.

Subgroup analyses

We will present the number and proportion of patients with adequate and inadequate antibody response in each disease subgroup. We will also present the number and proportion in each of these groups with COVID-19 infection and COVID-19 related hospitalisation. Provided there are sufficient numbers in each group, we will undertake exploratory analyses using the same approach as for the analysis of the primary outcome in the full cohort.

Exploratory Analyses

Evaluation of QCOVID4 risk score

i) Is the QCOVID4 score associated severe COVID-19 in our cohort? (low/med/high and quantitative analysis)

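### The adjusted infection models in Appendix 3 contain no calendar-time term, although booster dates and Visit 1 dates differ between participants

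*Protocol*

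**What the plan says.** Protocol section 11.0 refers the reader to Appendix 3 as the statistical analysis plan, so the covariates are set there.

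- **Primary model.** Logistic regression of infection on a binary antibody response, reported unadjusted and for "a model adjusted for the baseline and behavioural variables", together with any COVID-19 therapy given before or during a hospital stay.
- **Baseline variables.** "Demographics (Age, BMI, self-reported ethnicity, sex, Index of Multiple Deprivation"), then occupation and protective equipment, medical conditions, immunosuppression, "Vaccination history including COVID-19, influenza, and any test vaccines given", and known prior infection.
- **Behavioural variables.** Illness in a household contact that led to self-isolation: "we will collect data on the nature of that illness (when was illness, symptoms, severity, duration"). This dates a contact's illness; it does not place the participant's own follow-up in calendar time.
- **Time-to-event sensitivity analysis.** Competing-risk regression with the covariates of the primary model.
- **Visit 1 analysis.** A similar analysis, "with adjustment required for time post-vaccine to Visit 1, and also vaccine type pre-Visit 1", with infections described up to Visit 2.

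On timing, section 6.1 (Figure 1) defines Visit 1 as a "BASELINE visit at the time of recruitment (flexible time point but not within the 4 week period after vaccination"). Section 6.1 also allows recruitment before or after the booster and puts Visit 4 at 24 to 36 weeks after the dose.

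**The concern.** Two participants with the same antibody level and the same listed covariates can start follow-up in different months and so face different community incidence. If low responders are over-represented among those whose follow-up covers a high-incidence period, part of the season effect is credited to antibody status. If they are not, there is no bias of this kind. The model then simply leaves predictable variation unexplained, and predicted infection probabilities are miscalibrated for people who started earlier or later than average. Calibration matters here because Appendix 3 plans to judge the prediction model on those probabilities.

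Adjusting for time since vaccine in the Visit 1 analysis is only a partial substitute. People equally far from their last dose can still enter in different months.

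**Working it through.** **1. The plan's own figures.** With 750 low/no responders, 2250 normal responders, 90% power and 5% two-sided alpha, at a 50% rate the detectable difference is about (1.96 + 1.28) × √[0.25 × (1/750 + 1/2250)] = 3.24 × 0.0211 = 0.068. That is 56.8% against 50%, OR 1.32, standardised effect ln(1.32) × √3/π = 0.15. This matches the stated lower end of 0.15 and the claim of less than 10%. At 10% to 20% infection the detectable OR is about 1.5 to 1.4. These give a scale for any false OR.

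**2. Is calendar time anywhere in the covariates?** The lists above contain no dose date, entry date, variant period or background incidence. Vaccination history could be coded to include a date, but the text does not say so.

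**3. Size in the primary analysis.** The documents give no incidence by month, so this is an assumption: weekly hazard 0.3%, plus a bell-shaped rise (SD 6 weeks) to 1.2% at a late-December peak, with 26 weeks at risk starting two weeks after the dose. For a window from a to b weeks around the peak:

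H = 0.003 × 26 + 0.009 × 6 × √(2π) × [Φ(b/6) − Φ(a/6)], risk = 1 − exp(−H).

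- Earlier dose, a = −13.1, b = 12.9: H = 0.078 + 0.1354 × 0.970 = 0.209, risk 18.9%.
- Dose 12 weeks later, a = −1.1, b = 24.9: H = 0.078 + 0.1354 × 0.573 = 0.156, risk 14.4%.
- OR between dose dates: (0.189/0.811)/(0.144/0.856) = 1.39.

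Now take two equal halves, 25% low responders overall, no antibody effect within either half, and more low responders in the higher-risk half. For shares of 20% and 30%:

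- risk in low responders = (0.20 × 0.144 + 0.30 × 0.189)/0.50 = 17.1%
- risk in normal responders = (0.80 × 0.144 + 0.70 × 0.189)/1.50 = 16.5%
- false OR = (0.171/0.829)/(0.165/0.835) = 1.04.

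The same formula over a range of shares:

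| Low-responder share, lower- vs higher-risk half | False OR |
|---|---|
| 25% vs 25% | 1.00 |
| 22.5% vs 27.5% | 1.02 |
| 20% vs 30% | 1.04 |
| 18% vs 32% | 1.06 |

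The reverse imbalance gives false ORs below 1. The placement of the doses matters a little. With both doses three weeks later the risks are 18.7% and 12.1%, and the 20% vs 30% case gives 1.07. A period term removes the false OR in every row.

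**4. Visit 1 analysis.** Follow-up stops at Visit 2, which section 6.5.1 places ideally in the week before the booster. Under the same assumed curve, windows ending on 1 October have mean weekly hazards of about 0.31% (start 1 May) and 0.32% (start 9 July), which is almost no season contrast. Entry date also changes the length of the window, and that can push the OR the other way. At a flat 0.3% a week, 20 weeks gives 5.8% and 6 weeks 1.8%; with 20% low responders among early and 30% among late entrants, a crude null OR is about 0.86. Neither the sign nor the size of any bias after the planned adjustment can be fixed from the documents.

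**The case against.** The strongest reply is that the primary analysis is fairly well protected by design. Visit 3 is taken 4 to 10 weeks after the dose, so sampling does not tie antibody status to the calendar. Most doses belong to one autumn 2023 campaign, and a false OR of 1.02 to 1.06 is small beside a detectable OR of 1.3 to 1.5. The plan also adjusts the Visit 1 analysis for time since vaccine and vaccine type. All of this stands, and it is why the point is minor. What it does not answer is that dose dates still differ within the campaign and that no listed covariate captures them.

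Three stronger readings are tempting and are not supported.

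- A reader might compare 12 weeks from a May Visit 1 with 12 weeks from an early-October Visit 1. On the assumed curve that is 3.5% against 9.5% (OR 2.9), and with low-responder shares of 20% and 30% a crude null OR of 1.14. The schedule does not produce that comparison: follow-up ends at Visit 2, remote recruits after September 2023 may omit Visit 2 (section 6.5.1), and the face-to-face pathways in Appendix 6 go from Visit 1 to Visit 3 or 4. The 1.14 also precedes the planned adjustment for time since vaccine.
- A reader might cite larger illustrations, such as infection risk of 5% against 20% in two periods, which at 20% and 30% shares gives a false OR of 1.19. Nothing in the documents suggests so sharp a contrast between primary windows that overlap for months.
- A reader might take "depending on the prevailing population rates and the variant of interest" as the plan admitting that infection rates follow the wave. The clause concerns power for hospitalisation.

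**Conclusion.** The omission is real: no calendar-time term appears in the adjusted primary model, the competing-risk analysis or the Visit 1 analysis as Appendix 3 specifies them. In the primary analysis its main cost is precision and calibration, with a possible false OR of about 1.02 to 1.06. That range rests on an assumed seasonal hazard, doses 12 weeks apart, and low-responder shares that differ by 5 to 14 percentage points between earlier and later doses. With equal shares there is no bias. In the Visit 1 analysis bias is possible but unquantified. If a separate analysis plan already includes a calendar term, the point falls away.

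**What to change.** Add one sentence to Appendix 3. The adjusted primary logistic model and the time-to-event model include calendar month (or variant period) of the booster dose. The Visit 1 model includes calendar month of the Visit 1 date, alongside time since vaccine and vaccine type. State this before outcome data are analysed.

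The cost is low. Vaccination history and visits are already recorded, so no new data are needed. The change uses a few degrees of freedom; sparse months can be merged. In the Visit 1 model, month and time since vaccine will be partly collinear, so some widening of intervals there should be expected and reported.

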Assuming serology is predictive of outcome, we will build a model to explore the predictive value of key patient data and the added value of serological results. We will explore the discrimination and calibration of a model only including baseline and behavioural variables compared to this model also including serological response. Discrimination will be determined by Harrell's C statistic and calibration will be determined by the predicted probabilities for infection. It is not possible to externally validate this model in this study; instead 1000 bootstrapped samples will be used in determining the 95% confidence intervals for the C statistic.

As a sensitivity analysis we will also consider serological response as a continuous variable. We will also consider time to first infection as a time to event outcome with death as a competing risk. This will be implemented in Stata using the *stcrreg* command. The same covariates will be included in the adjusted model as for the primary analysis. Unadjusted and adjusted analyses will present hazard ratios with 95% confidence intervals.

To assess the additive value of serological responses to CV status in predicting severe outcome We will undertake an analysis using the same modelling approach as for the primary outcome but with a composite outcome of severe infection (infection, hospitalisation or death).

Secondary Outcomes

To evaluate the serological vaccine responses of CV patients to new vaccines

28-day post vaccine (Visit 3) IgG antibody levels (BAU/ml) will be reported in HC and CV individuals. The proportion of combined and individual CV groups with no, low or normal Visit 3 antibody levels will be reported.

The median (IQR) of Visit 3 antibody levels in each CV group will be reported, alongside the values for HC.

Logistic regression models will be used to assess factors that contribute to serological response as a binary outcome with normal compared to lack of response (no/low). The model will include the baseline variables set out in **Section 5.2** and further variables may be added to the model if evidence emerges that such variable impacts on vaccine responses to vaccines. Univariable logistic regression will be used to explore the unadjusted relationship of each variable with the outcome and multivariable logistic regression will be used to explore the independent relationship of each variable with the outcome. We will report odds ratios and 95% confidence intervals for all models.

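### The adjusted infection model controls for COVID-19 therapy with no limit to therapy given before the outcome window, so it conditions on a consequence of the outcome and can bias the antibody odds ratio in either direction

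*Protocol*

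**What the plan says.** All of this is in protocol section 23.0, Appendix 3.

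- **Primary model.** It is a "logistic regression model with infection as the outcome and antibody response post-V3 as a binary variable as the exposure". The outcome counts "all infections from ≥14 days post vaccination given between Visit 2 until Visit 4".
- **Reporting.** The plan states: "We will present odds ratios with 95% confidence intervals for the unadjusted model". It also reports an adjusted model with the baseline and behavioural variables "as well as any COVID-19 therapy received in the community, preadmission and in hospital (where data available". Neither estimate is ranked above the other.
- **Behavioural variables.** Under this head the plan states: "If the participant self-isolated as a result of an illness in a household contact, we will collect data on the nature of that illness". The date of that illness is among the items collected, but no time limit is set on its use as a covariate.
- **Competing-risk sensitivity analysis.** "The same covariates will be included in the adjusted model as for the primary analysis".
- **Severe outcome.** It is analysed "using the same modelling approach as for the primary outcome but with a composite outcome of severe infection (infection, hospitalisation or death".
- **Discrimination and calibration.** The comparison is of "a model only including baseline and behavioural variables compared to this model also including serological response". Therapy is not named here.

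**The concern.** The settings named for therapy (community, before admission, in hospital) are those in which a COVID-19 episode is treated. Such treatment comes after the infection that the model is meant to explain. Treated participants are then nearly all cases, while untreated participants are a mix of cases and non-cases. Adjusting for this variable does not remove confounding. It sets aside the treated infections and compares antibody groups on what is left.

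If treatment uptake differs between antibody groups, the treated infections are removed unevenly and the adjusted OR moves away from the true value. What is at stake is the only confounder-adjusted estimate of the primary association, together with the adjusted models that copy its covariates. This is a covariate choice that the document states outright, not a detail left open for later.

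Household illness raises a smaller question of timing. An illness in the household during the outcome window may belong to the same transmission event as the participant's own infection.

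**Working it through.** **1. The plan's own figure.** Appendix 3 assumes 750 low or non-responders and 2250 normal responders, 90% power and a two-sided 5% level, with 50% as the most conservative rate. Taking 50% as the rate in the normal group, the detectable difference is 6.8 percentage points: 56.8% against 50%, OR 1.315. The standardised effect is ln(1.315) × √3/π = 0.151. This agrees with the stated difference below 10% and the stated lower bound of 0.15. The upper bound of 0.36 would correspond to a rate between 3% and 4%, but the rates used are not shown, so it cannot be confirmed.

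**2. Formula.** Let p be the infection risk in an antibody group and t the share of its infected members who receive therapy. Suppose first that therapy is recorded only in infected participants. Having therapy then predicts infection perfectly. Whether the software drops those participants or lets the therapy coefficient diverge, the antibody coefficient comes from the untreated:

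adjusted OR = [p_low(1 − t_low)/(1 − p_low)] / [p_normal(1 − t_normal)/(1 − p_normal)] = true OR × (1 − t_low)/(1 − t_normal).

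**3. Numbers.** The documents give no uptake figures, so the values of t are assumptions shown as a range. Also assumed are 20% infection in normal responders and a true OR of 1.50. The odds in low responders are then 0.25 × 1.5 = 0.375, so p_low = 0.375/1.375 = 27.3%. Expected infections are 2250 × 0.20 = 450 and 750 × 0.273 = 204.5, about 655 in all. Infections left in the fit are 450(1 − t_normal) + 204.5(1 − t_low).

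| Uptake normal / low | Factor | Adjusted OR | Infections left of 655 |
|---|---|---|---|
| 30% / 30% | 1.00 | 1.50 | 458 |
| 10% / 20% | 0.89 | 1.33 | 569 |
| 20% / 40% | 0.75 | 1.125 | 483 |
| 40% / 60% | 0.67 | 1.00 | 352 |
| 20% / 60% | 0.50 | 0.75 | 442 |
| 40% / 20% | 1.33 | 2.00 | 434 |

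Check of the 20%/40% row from counts: (122.7/545.5)/(360/1800) = 0.225/0.200 = 1.125.

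**4. Simulation.** For each setting, 400 data sets of 750 + 2250 were generated.

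- True OR 1.50, uptake 20%/40%: without the therapy term the OR is 1.49 and significant in 98% of data sets. With it, the OR is 1.12 and significant in 18%.
- True OR 1.50, uptake 40%/20%: the OR with the term is 1.98.
- True OR 1.50, uptake 30%/30%: the OR with the term is 1.50.
- Infection 50% in normal responders, true OR 1.317, uptake 20%/40%: the OR falls to 0.99, and significant results fall from 92% to 4%.
- No true association, uptake 20%/40%: the OR is 0.75, and 63% of data sets are falsely significant.
- True OR 1.50, uptake 20%/40%, with 1% of uninfected participants also having therapy recorded: there is no perfect prediction, but the OR is still 1.19.

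**5. Where the term travels.** The competing-risk model takes the same covariates, so therapy there post-dates the event being modelled. The closed form above is for the logistic model, and the size of the error in the hazard ratio was not computed. The composite counts infection itself, so therapy again conditions mainly on infection.

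**6. Timing of covariates.** Infections count from day 14 after vaccination, while section 6.1 places Visit 3 at 4 to 10 weeks after the dose. Covariates dated up to the Visit 3 sample could therefore still post-date a counted infection. The safe limit is the opening of the outcome window.

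**The case against.** Several points on the other side are fair.

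- **The unadjusted OR is reported and contains no therapy term.** This stands. A reader might infer that the adjusted OR is the study's main result, but the document does not rank the two.
- **The predictive comparison is separate.** A reader might infer that the prediction model is also spoiled. As described, it holds only baseline and behavioural variables, with and without serology. The therapy objection does not reach it, and only the dating of household illness does.
- **Therapy need not be confined to infected participants.** Section 5.3 recognises pre-exposure prophylaxis and excludes monoclonal antibodies only within 26 weeks before the first sample. Therapy for an earlier episode might also be recorded. Prediction may then be imperfect. This softens the bias without removing it (1.19 rather than 1.12 in the simulation).
- **Uptake may not differ.** Every participant is clinically vulnerable, and the documents do not say that low responders are treated more often. A reader might infer that the adjusted OR is certainly wrong, or certainly pulled towards 1. Neither follows: equal uptake gives no bias, and reversed uptake inflates the OR.
- **Household illness is an exposure, not by definition a consequence of infection**, and its date is to be collected. This stands, so the point there is limited to timing.

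None of this supplies a reason to have treatment of the episode in a model whose outcome is that episode.

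**Conclusion.** The concern holds for the therapy term in the adjusted infection model, the adjusted competing-risk model and the adjusted composite model. As written, these condition on a variable that largely follows the outcome. That the problem exists rests on the wording of the plan. Its size and direction rest on uptake by antibody group, which the documents do not give. Over the assumed range, a true OR of 1.50 is reported as anything from 0.75 to 2.00. Only equal uptake leaves it unbiased, and at 30% uptake in both groups about 30% of the infections (655 to 458) still drop out of the fit. The adjusted estimate could therefore hide, reverse, exaggerate or create an association, and the reader could not tell which.

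**What to change.** 1. Delete the therapy clause from the adjusted infection, competing-risk and composite models. Keep only prophylaxis or therapy given before the outcome window opens, 14 days after vaccination.
2. Use household-illness variables in the adjusted and prediction models only when the illness is dated before that window opens, using the illness date already collected.
3. If treatment of the episode is of interest, examine it in a separate analysis of severity among infected participants. Do not adjust for in-hospital therapy when hospitalisation is the outcome.

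The cost is one clause removed and one date restriction added, with no extra visits or samples. Therapy dates are needed only for the retained pre-window term. If they are not available, that term can be dropped.

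### The comparison of C with and without serology has no confidence interval for the change in C, the quantity that measures added value

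*Protocol*

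**What the plan says.** Section 11.0 of the protocol refers the reader to Appendix 3 as the statistical analysis plan. Under Primary Outcome, that appendix states the aim as "To assess the additive value of serological responses to CV status in predicting infection".

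The primary analysis is a "logistic regression model with infection as the outcome and antibody response post-V3 as a binary variable as the exposure". Odds ratios with 95% intervals are given unadjusted, "as well as for a model adjusted for the baseline and behavioural variables as well as any COVID-19 therapy received".

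A prediction step follows, on a condition: "Assuming serology is predictive of outcome, we will build a model to explore the predictive value of key patient data". The comparison is then set out: "We will explore the discrimination and calibration of a model only including baseline and behavioural variables compared to this model also including serological response". The measures are named: "Discrimination will be determined by Harrell's C statistic and calibration will be determined by the predicted probabilities for infection". External validation is said to be impossible in this study, and the replacement is: "instead 1000 bootstrapped samples will be used in determining the 95% confidence intervals for the C statistic".

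No interval or test for the difference between the two C statistics is mentioned. The severe-outcome analysis reuses the same approach. By contrast, the QCOVID4 item on adding serology (Exploratory Analyses, item iv) does plan a test of the nested models, without saying which test.

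**The concern.** Added value is a contrast between two models fitted to the same people, so the relevant null is a change in C of zero. An interval for one model's C shows how well that model's discrimination is known. It does not show how well the gain is known, because the two C statistics share the same participants and move together from sample to sample.

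The planned output therefore leaves a reader with two poor options. Comparing the point estimates ignores sampling error. Comparing the two intervals by eye ignores the correlation and is very insensitive. Optimism correction of each C would not close this gap, because it corrects the level of each C and gives no precision for the difference.

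**Working it through.** **Inputs from the protocol (Appendix 3).** 3000 participants, split 750 no/low response and 2250 normal response; two-sided 5% level; 90% power; nested models; Harrell's C, which equals the area under the ROC curve for a binary outcome; 1000 resamples.

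**The plan's own figure.** The appendix gives no value for C or its change, so the only figures to reproduce are those for sample size. With 750 v 2250, 90% power and 50% infection, the detectable difference is 6.8 percentage points, an odds ratio of 1.315. The standardised effect is ln(1.315) × √3/π = 0.274 × 0.551 = 0.151, against the stated 0.15. At 20% infection the detectable difference is 5.7 points (odds ratio 1.384). Both are below the stated 10 points, so this part of the plan reproduces.

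**Assumptions for the check.** The documents give no infection rate, odds ratio or C. Assumed: 25% low response (the plan's split); 10 baseline covariates giving C of about 0.64 without serology; infection risk of 20% (or 10%) in a normal responder with average covariates; serology odds ratios from 1.0 to 3.0. Both logistic models were refitted on every resample. The change in C was not optimism-corrected.

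**One scenario by hand (20%, odds ratio 2.0, N=3000).** Mean C goes from 0.638 to 0.662, a change of 0.024. The SE is 0.0115 for C (model without serology, taken as equal for both) and 0.0067 for the paired change.

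- Separate intervals: 0.638 ± 1.96 × 0.0115 = 0.615 to 0.661, and 0.662 ± 0.0225 = 0.639 to 0.685. They overlap.
- Change needed for no overlap: 2 × 1.96 × 0.0115 = 0.045, nearly twice the gain.
- Paired interval: 0.024 ± 1.96 × 0.0067 = 0.011 to 0.037. It excludes 0.
- Implied correlation of the two C statistics: 1 − 0.0067² / (2 × 0.0115²) = 0.83.

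**Simulation results.** The last four columns give the share of cohorts in which each criterion shows a gain.

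| Infection, OR, N | Change in C | SE of C | SE of change | Separate intervals do not overlap | Paired percentile interval excludes 0 | Paired normal interval excludes 0 | LR test p<0.05 |
|---|---|---|---|---|---|---|---|
| 20%, 1.384, 3000 | 0.0046 | 0.0118 | 0.0031 | 0% | 53% | 12% | 78% |
| 20%, 2.0, 3000 | 0.0240 | 0.0115 | 0.0067 | 0% | 100% | 100% | 100% |
| 10%, 2.0, 3000 | 0.0245 | 0.0146 | 0.0085 | 0% | 100% | 88% | 100% |
| 20%, 2.0, 2000 | 0.0252 | 0.0140 | 0.0082 | 0% | 100% | 93% | 100% |
| 20%, 3.0, 3000* | 0.0552 | 0.0113 | 0.0088 | 93% | 100% | 100% | 100% |
| 20%, 1.0, 3000* | 0.0007 | 0.0120 | 0.0015 | 0% | 3% | 0% | 5% |

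Rows without an asterisk use 40 cohorts and 1000 resamples; rows with one use 60 cohorts and 150 resamples. A 60-cohort run of the second row gave 3% non-overlap. Monte Carlo error is up to √(0.25/40), about 8 percentage points.

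**What the table shows.** The change is estimated more tightly than either C in every row. Near the null, the result depends on the type of paired interval (53% v 12% at odds ratio 1.384), and both types fall short of the likelihood-ratio test (78%).

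**The case against.** The strongest reply is that the text contains no bad decision rule. A reader might infer that added value will be judged by whether two intervals overlap, and hence that a real gain will be hidden. The appendix supports neither step. It gives no overlap criterion or threshold, describes the comparison as exploratory, and does not rule out reporting the difference. The non-overlap figures above show what that reading would cost, not what the plan prescribes.

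Second, the primary adjusted odds ratio largely tests whether serology carries information beyond patient data. The likelihood-ratio column suggests that such a test is at least as sensitive as an interval for the change in C. This stands, and it is why the existence of a gain is not at risk. It does not supply the missing quantity: an odds ratio measures association, not gain in discrimination. Nor is the adjusted model the same as the prediction model, since it also includes COVID-19 therapy, some of which follows the infection being predicted.

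Third, a reader might worry that a useless marker would look helpful, because apparent C tends to rise when any variable is added. The prediction model is built only if serology is already predictive, so null results for all cohorts do not apply directly.

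Fourth, this could be called a detail for a separate analysis plan. But the protocol names Appendix 3 as that plan, and the appendix already fixes the number of resamples and their target. It also plans a nested-model test for QCOVID4 but not here.

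**Conclusion.** The point holds as an inexpensive improvement to an exploratory, conditional step. The plan sets out to measure added value and gives no precision for the measure that expresses it. What is lost is the precision of the gain in discrimination, not evidence that the gain exists.

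With the assumed 20% infection, odds ratio 2.0 and C of about 0.64 without serology, the gain of about 0.024 has an SE of 0.0067, against 0.0115 for each C. The contrast between the two readings is not universal: at an odds ratio of 3.0 the separate intervals already fail to overlap in 93% of cohorts. All these sizes rest on assumed rates, odds ratios and covariate strength. The gap in the text does not depend on them.

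**What to change.** In Appendix 3, Primary Outcome, amend the bootstrap sentence to say the following:

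- Both models are fitted to the same participants, namely those with complete data for the larger model, and both are refitted on each of the 1000 resamples.
- The estimate of added value is the change in C (with minus without serology), corrected for optimism, with its 95% interval. The type of interval is named in advance, because the types differ when the gain is small.
- Significance is assessed by a likelihood-ratio test of the nested models, in line with the nested-model test planned for QCOVID4. The interval for the change in C describes precision and is not used as the test, because it is poorly calibrated near the null.
- The same applies to the severe-outcome model.

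The separate intervals for each C can stay as description. The cost is a few sentences and a few lines of code. The resamples are already planned and no new data are needed.
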